## CONFIDENTIAL

201789

Procedures	Screening	Baseline		Treatment Period										FU	EW 											
	Visit														Last Visit											
	1	2	3	4	5	6	7	8	9	10	11	12	13	14	15											
	Week																									
	(up to 4 weeks)	0	1	2	3	4	6	8	10	12	15	18	22													
	Day																									
		1	3*	8	15	22	29	43	57	71	74*	85	106	127	155											
Allowance				±1 day				±3 days			±1 day	±3 days	±1 week													
Safety Evaluations 																										
Concomitant Medication	X	X	Record all concomitant medications																							
Height  , Body weight	X						X					X			X	X										
Other Physical Examination 	X	X 		X	X		X		X			X			X	X										
Vital Signs	X	X		X	X	X	X	X	X			X			X	X										
12-lead ECG 	X											X				X										
AEs/SAEs/AESIs	X 	X	X	X	X	X	X	X	X	X	X	X	X	X	X	X										
Cough, Lung Auscultation, Pulse Oximetry, Borg Dyspnea Scale	X	X 		X	X	X	X	X	X			X			X	X										
Chest X-ray 	X																									
Spirometry (FEV 1 , FVC)	X											X			X	X										
D LCO	X 											X			X	X										
Laboratory Assessments																										
Hematology, Chemistry (except for lipid and pregnancy test)	X	X 			X		X		X			X			X	X										

## CONFIDENTIAL

201789

Procedures	Screen-ing	Baseline		Treatment Period										FU	Last Visit	EW 
	Visit															
	1	2	3	4	5	6	7	8	9	10	11	12	13	14	15	
	Week															
	(up to 4 weeks)	0	1	2	3	4	6	8	10	12	15	18	22			
	Day															
		1	3*	8	15	22	29	43	57	71	74*	85	106	127	155	
Allowance			±1 day					±3 days			±1 day	±3 days	±1 week			
Urinalysis (dip stick)	X						X		X			X			X	X
Cholesterol, triglycerides, HDL, LDL 		X 										X			X	X
Pregnancy test 	S	U					U		U			U			U	U
TB, HBsAg, HepB cAb, HBs Ab, HepC Ab, HIV, HBV DNA **	X															
HBV DNA monitoring (HBs Ab positive subject only)							X		X			X	X	X	X	X
RF, ACPA (anti-CCP)	X															
ESR 		X 		X	X		X	X	X			X			X	X
CRP	X	X 		X	X		X	X	X			X			X	X
Other Laboratory Assessments																
PK blood sampling (GSK3196165) 		X 	X	X	X		X		X	X	X	X	X	X	X	X
Free GM-CSF, GM-CSF-GSK3196165 complex		X 	X	X	X		X		X	X		X			X	X
PD blood biomarkers		X 			X		X					X				X
RNA blood biomarker		X 										X			X	X

## CONFIDENTIAL

201789

Procedures	Screening	Baseline		Treatment Period										FU	EW 	
	Visit														Last Visit	
	1	2	3	4	5	6	7	8	9	10	11	12	13	14	15	
	Week															
	(up to 4 weeks)	0	1	2	3	4	6	8	10	12	15	18	22			
	Day															
	1	3*	8	15	22	29	43	57	71	74*	85	106	127	155		
Allowance			±1 day					±3 days			±1 day	±3 days	±1 week			
PGx sampling DNA 		X 														
Lung biomarkers		X 										X		X	X	
Immunogenicity (anti-GSK3196165 antibody) 		X 			X		X					X		X	X	
Anti-GM-CSF auto-antibodies		X 														
Study Treatment GSK3196165/placebo 		X		X	X	X	X	X	X							

ACPA: Anti-cyclic citrullinated protein antibody, CCP: Cyclic citrullinated peptide, ESR: Erythrocyte sedimentation rate, FVC: Forced vital capacity, HBV: Hepatitis B virus, HDL: High-density lipoprotein, LDL: Low-density lipoprotein, RF: Rheumatoid factor.

1. All subjects who withdraw from the study should have an early withdrawal (EW) visit as soon as possible after study agent discontinuation and then return for a follow-up visit (the last visit) for 10 weeks

(12 weeks after last dose of study medication).

2. The same individual (where possible) should perform all disease assessments for an individual subject.

3. PRO assessments should be conducted before any tests, procedures, assessments or consultations, to avoid influencing the subjects' perception.

4. Assessments may be performed up to 24hours before dosing GSK3196165/placebo.

5. All safety evaluations should be conducted before dosing GSK3196165/placebo.

6. Height will be measured at only screening.

7. Complete physical at screening, and then limited physical examination (see Section 7.4.7 in the Protocol) thereafter.

8. ECG should be performed before vital signs, blood draws, and dosing (triplicate ECGs required at screening, and single thereafter unless there are safety concerns, in which case repeats may be required  
(see Section 7.4.9 in the Protocol).
9. Only SAEs related to study participation or related to a GSK product will be recorded from the time a subject consents to participate in the study.
10. Unless performed within previous 12 weeks (No need to repeat if subject re-screened).
11. Chest HRCT if  $D_{LCO} \geq 60\% - <70\%$  predicted (No need to repeat if subject re-screened).
12.  $\geq 8$  hours fasting required before blood draw.
13. For women of child-bearing potential. S=serum; U=urine.
14. ESR measured locally.
15. PK sampling should be collected before dosing at the visits scheduled study treatment (GSK3196165/placebo). At the visits doesn't scheduled study treatments, it may be collected in any time during the visit. (Day 3, 74, 85, 106, 127, 155, and early withdrawal visit).
16. In consenting subjects.
17. In addition to these scheduled immunogenicity assessments, "event-driven" testing will also be employed for those subjects that experience anaphylaxis, serious hypersensitivity, or AEs related to study drug administration that led to withdrawal from the study (see Section 7.5 in the Protocol).
18. GSK3196165 or placebo must be administered on the same day each week  $\pm 1$  day for the first 5 weekly doses, thereafter on the same day EOW  $\pm 3$  days for bi-weekly doses.  
\* The Day 3 (Visit 3) blood sample must be drawn 2 days ( $\pm 1$  day is allowable) after the first dose, and the Day 74 (Visit 11) blood sample must be drawn 3 days ( $\pm 1$  day is allowable) after the last dose.  
\*\* HBV-DNA sample will be collected from all subjects, and HBV-DNA will be tested for only subjects with HBs Ab positive.

**11.2. Appendix 2: Assessment Windows**

Data at the scheduled visit defined by Appendix 1 will be summarized according to this RAP. Data out of the allowances will not be slotted to a particular time point, but will be listed as unscheduled and early withdrawal unless otherwise specified.

[figure not shown]
In case that the one allowance contains more than two assessments, the first assessment will be treated as the scheduled and the others as the unscheduled.

### 11.3. Appendix 3: Treatment States and Phases

#### 11.3.1.1. Treatment States for Concomitant Medications for Rheumatoid Arthritis (CONMEDS RA) Data

Treatment State	Definition
Prior only	CONMEDs RA Stop Date < the Date of first dose of study medication
Prior and Concomitant	CONMEDs RA Start Date < the Date of first dose of study medication CONMEDs RA Stop Date $\geq$ the Date of first dose of study medication
Concomitant only	CONMEDs RA Start Date $\geq$ the Date of first dose of study medication

#### Flowchart

### 11.3.1.2. Treatment States for AE Data

Treatment State	Definition
Pre-Treatment	AE Start Date < Study Treatment Start Date
On-treatment	Study Treatment Start Date ≤ AE Start Date ≤ Study Treatment Stop Date + 12 weeks
Post-treatment	AE Start Date > Study Treatment Stop Date + 12 weeks
Onset Time Since 1 st Dose (Days)	If Treatment Start Date > AE Onset Date, = AE Onset Date - Treatment Start Date If Treatment Start Date ≤ AE Onset Date, = AE Onset Date - Treatment Start Date + 1 Missing otherwise.
Onset Time Since last Dose (Days)	If Treatment Stop Date > AE Onset Date, = AE Onset Date - Treatment Stop Date If Treatment Stop Date ≤ AE Onset Date, = AE Onset Date - Treatment Stop Date + 1 Missing otherwise
Duration (Days)	AE Resolution Date – AE Onset Date + 1
Drug-related	If relationship to GSK3196165/Placebo is marked 'YES' on Inform/CRF OR value is missing.
MTX-related	If relationship to Methotrexate is marked 'YES' on Inform/CRF OR value is missing.

**NOTES:**

- If the study treatment stop date is missing then the AE will be considered to be On-Treatment.

## 11.4. Appendix 4: Data Display Standards & Handling Conventions

### 11.4.1. Study Treatment & Sub-group Display Descriptors

Treatment Group Descriptions			
RandAll NG		Data Displays for Reporting	
Code	Description	Description	Order [1]
A	Placebo	Placebo	1
B	GSK3196165 45 mg	GSK3196165 45 mg	2
C	GSK3196165 90 mg	GSK3196165 90 mg	3
D	GSK3196165 180 mg	GSK3196165 180 mg	4

**NOTES:**

1. Order represents treatments being presented in TFL, as appropriate.

### 11.4.2. Baseline Definition & Derivations

#### 11.4.2.1. Baseline Definitions

For all endpoints (expect as noted in baseline definitions) the baseline value will be the latest pre-dose assessment.

#### 11.4.2.2. Derivations and Handling of Missing Baseline Data

Definition	Reporting Details
Change from Baseline	= Post-Dose Visit Value – Baseline
% Change from Baseline	= $100 \times [(Post-Dose Visit Value – Baseline) / Baseline]$

**NOTES :**

- Unless otherwise specified, the baseline definitions specified in Section 11.4.2.1 Baseline Definitions will be used for derivations for endpoints / parameters and indicated on summaries and listings.
- Unless otherwise stated, if baseline data is missing no derivation will be performed and will be set to missing.
- The baseline definition will be footnoted on all change from baseline displays.

### 11.4.3. Reporting Process & Standards

Reporting Process	
Software	

 
• The currently supported versions of SAS software will be used.
 
	
Reporting Area	
HARP Server	:uk1salx00175
HARP Area	:arenv\arprod\gsk3196165\mid201789\final_02
QC Spreadsheet	:arenv\arprod\gsk3196165\mid201789\final_02\qc

Reporting Process
Analysis Datasets

 
Analysis datasets will be created according to Legacy GSK A&R dataset standards OR CDISC standards (SDTM IG Version 3.1.3 & AdaM IG Version 1.0).
 
For creation of ADaM datasets (ADCM/ADAE), the same version of dictionary datasets will be implemented for conversion from SI to SDTM.
 

Generation of RTF Files

 
RTF files will not be generated.
 

Reporting Standards
General

 
The current GSK Integrated Data Standards Library (IDSL) will be applied for reporting, unless otherwise stated: 
 
4.03 to 4.23: General Principles
 
5.01 to 5.08: Principles Related to Data Listings
 
6.01 to 6.11: Principles Related to Summary Tables
 
7.01 to 7.13: Principles Related to Graphics
 
 
 

Formats

 
All data will be reported according to the randomized group the subject received unless otherwise stated.
 
GSK IDSL Statistical Principles (5.03 & 6.06.3) for decimal places (DP's) will be adopted for reporting of data based on the raw data collected.
 
Numeric data will be reported at the precision collected on the eCRF.
 
The reported precision from non eCRF sources will follow the IDSL statistical principles but may be adjusted to a clinically interpretable number of DP's.
 

Planned and Actual Time

 
Reporting for tables, figures and formal statistical analyses : 
 
Planned time relative to dosing will be used in figures, summaries, statistical analyses and calculation of any derived parameters, unless otherwise stated.
 
The impact of any major deviation from the planned assessment times and/or scheduled visit days on the analyses and interpretation of the results will be assessed as appropriate.
 
 
 
Reporting for Data Listings: 
 
Planned and actual time relative to study drug dosing will be shown in listings (Refer to IDSL Statistical Principle 5.05.1).
 
Unscheduled or unplanned readings will be presented within the subject's listings.
 
Visits outside the protocol defined time-windows (i.e. recorded as protocol deviations) will be included in listings but omitted from figures, summaries and statistical analyses.
 
 
 

Unscheduled Visits

 
Unscheduled visits will not be included in summary tables, except for the Respiratory events and the laboratory items which may be re-tested.
 
Unscheduled visits will not be included in figures.
 
All unscheduled visits will be included in listings.
 

Reporting Standards	
Descriptive Summary Statistics	
Continuous Data	Refer to IDSL Statistical Principle 6.06.1
Categorical Data	N, n, frequency, %
Reporting of Pharmacokinetic Concentration Data	
Descriptive Summary Statistics	Refer to IDSL Statistical Principle 6.06.1 Assign zero to NQ values (Refer to GUI_51487 for further details)
Reporting of Pharmacokinetic Parameters	
Descriptive Summary Statistics (Log Transformed)	N, n, geometric mean, 95% CI of geometric mean, standard deviation (SD) of logged data and [between and or within] geometric coefficient of variation (CV b/w (%)) will be reported. [1] $CV_b (\%) = \sqrt{(\exp(SD^2) - 1) * 100}$ (SD = SD of log transformed data)
Parameters Not Being Log Transformed	T max
Graphical Displays	

 
Refer to IDSL Statistical Principals 7.01 to 7.13.
 
	

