9.4.4. Efficacy Analyses

The ITT population with observed case dataset will be used for efficacy analyses. Time course of the change from baseline in DAS28(CRP) will be analyzed by mixed model for repeated measurements (MMRM). The dose response analyses will be performed on the change from baseline in DAS28(CRP) at Week 12. Full details for all efficacy analyses will be given in the RAP.

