### 2.1. Changes to the Protocol Defined Statistical Analysis Plan

There were no changes or deviations to the originally planned statistical analysis specified in the protocol [(Dated: 27/SEP/2016)].

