**8.2.2. DAS28 (CRP)**

DAS28(CRP) values will be listed and summarized by dose group and nominal time. Mean and Median change from baseline versus time profile by dose group will be plotted.

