#### 11.5.4. Efficacy

ACR 20/50/70 response [American Collenge of Rheumatology Committee to Reevaluate Improvement Criteria, 2007]
Procedure

• The following 7 ACR-core set measures will define ACR20/50/70 response.

• Tender/Painful Joint Count 68 (TJC68)

• Swollen Joint Count 66 (SJC66)

• Patient's Assessment of Arthritis Pain at this time

• Patient's Global Assessment of Arthritis

• Physician's Global Assessment of Arthritis

• C-reactive protein (CRP) (in mg/L)

• Health Assessment Questionnaire-Disability Index (HAQ-DI)

• The %Change from Baseline in each ACR-core set measure will be calculated.

• If %Change from Baseline in both tender and swollen joint counts are less than -20% and those in 3 of the 5 remaining ACR-core set measures are less than -20%, ARC20 criteria is met.

• Similarly ACR50 and 70 are calculated with the respective percent improvement.

• For all visits if any of the component scores are missing, then those scores will considered as not having met the criteria for improvement. Therefore, if TJC68 or SJC66 or 3 or more of the 5 remaining ACR-core set measures are missing, ACR20/ ACR50/ ACR70 will each be considered as "no response"

• For component scores with missing Baseline values or a Baseline value of 0, the percentage improvement cannot be calculated and the component will be considered as not having met the criteria for improvement for all visits.

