### Categorical DAS28 Response

- DAS28 (CRP) and DAS28 (ESR) will be categorized using EULAR response criteria. Response at a given time point is defined based on the combination of current DAS28 score and DAS28 decrease from baseline. The definition of no response, moderate response and good response is captured in the following table:
- DAS28 decrease from baseline value will be calculated using the following formula:

$$\text{DAS28 decrease from baseline} = \text{DAS28 Baseline} - \text{Post-Dose Visit DAS28 Value}$$

Current DAS28	DAS28 decrease from baseline		
	>1.2	>0.6 to $\leq 1.2$	$\leq 0.6$
$\leq 3.2$	Good response	Moderate response	No response
$>3.2$ to $\leq 5.1$	Moderate response	Moderate response	No response
$>5.1$	Moderate response	No response	No response

- If the post-baseline DAS28 (CRP) or DAS28 (ESR) is missing, then the corresponding EULAR category will be missing.

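### A scheduled Week 12 efficacy assessment done outside the ±3-day visit allowance is listed but not analysed, and the SAP does not say how it is scored in the responder endpoints

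*SAP*

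**What the plan says.** **Windows.** The Time and Events tables (Protocol 7.1, SAP 11.1.1) put Week 12 at Day 85 with an allowance of ±3 days. SAP 11.2 says: "Data out of the allowances will not be slotted to a particular time point". Such data are listed as unscheduled or early-withdrawal records. SAP 11.4.3 adds: "Visits outside the protocol defined time-windows (i.e. recorded as protocol deviations) will be included in listings but omitted from figures, summaries and statistical analyses". The only exceptions, which let an unscheduled visit into a summary table, are for respiratory events and re-tested laboratory items. For major timing deviations, SAP 11.4.3 says that the impact "on the analyses and interpretation of the results will be assessed as appropriate", and names no analysis.

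**Continuous endpoints.** SAP 8.2.2: "DAS28(CRP) values will be listed and summarized by dose group and nominal time". SAP 11.6.2 imputes nothing, and SAP 11.6.2.2 assumes missing at random.

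**Binary endpoints.** SAP 11.6.2 describes missing data as requested data not provided, leaving blank fields. It then imputes missing efficacy data or early withdrawal as failure, with DAS28(CRP) non-remission and EULAR non-response as examples. In SAP 11.5.4 the ACR rule is: "For all visits if any of the component scores are missing, then those scores will considered as not having met the criteria for improvement". A missing DAS28 counts as no remission. For EULAR: "If the post-baseline DAS28 (CRP) or DAS28 (ESR) is missing, then the corresponding EULAR category will be missing".

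**Several values in one window.** SAP 11.2 takes the first when an allowance holds more than two assessments. SAP 11.5.1 takes the value closest to target when there are two, with the mean for ties, and in a separate bullet takes the mean of multiple measurements.

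**Protocol.** Section 9.4.4: "The ITT population with observed case dataset will be used for efficacy analyses". It leaves full details to the RAP. SAP 2.1: "There were no changes or deviations to the originally planned statistical analysis specified in the protocol".

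**The concern.** A visit allowance tells sites when to book the patient. Here it also decides which measured outcomes count. A patient seen one day late has a valid DAS28(CRP), but the value appears only in a listing.

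The responder endpoints raise a second problem. Every rule the SAP gives for them concerns missing data, and a Day 89 value is not missing under the SAP's own definition. A programmer must therefore decide whether that subject is a responder, a failure or outside the count. The natural choice, treating the value as missing, turns an observed response into a failure. With 10 subjects per arm, one such decision is visible in the reported rate.

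**Working it through.** **1. The plan's own precision figure.** The only one is Protocol 9.2, Table 4: exact 95% intervals for 1, 2 and 3 events in 10. The Clopper-Pearson formula gives 0.25–44.50%, 2.52–55.61% and 6.67–65.25% (upper limit 65.245% before rounding), which agrees with the table. This point does not depend on it.

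**2. Does Day 89 fall in any efficacy window?** Target day ± allowance:
- Day 8: 7–9
- Day 15: 14–16
- Day 29: 28–30
- Day 43: 40–46
- Day 57: 54–60
- Day 85: 82–88
- Day 155: 148–162

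Day 89 is in none of them, and the next window opens on Day 148. The allowance row is broken in the extracted text. Its order, and the separate ±1 day footnote for Day 74, support ±3 days for Day 85.

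**3. Responder endpoints.** Assumed example: 6 of 10 measured responders on active treatment and 3 of 10 on placebo, with the normal-approximation interval that the SAP specifies, d ± 1.96·√(p₁q₁/n₁ + p₂q₂/n₂).
- All values used: 6/10 − 3/10 = 30.0 points; √(0.024 + 0.021) = 0.2121; 95% CI −11.6 to 71.6.
- One late active responder scored as failure: 5/10 − 3/10 = 20.0 points; √(0.025 + 0.021) = 0.2145; 95% CI −22.0 to 62.0.
- One late placebo responder scored as failure: 6/10 − 2/10 = 40.0 points; √(0.024 + 0.016) = 0.2000; 95% CI 0.8 to 79.2.

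The shift is 1/10 = 10 points per subject, downward or upward according to the arm.

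**4. Continuous endpoints, one Week 12 value lost in one arm.**
- Simple difference from placebo: SE ratio √[(1/9 + 1/10)/(2/10)] = 1.027, or +2.7%.
- MMRM, taken as generalised least squares with known compound symmetry, correlation ρ (assumed) and six visits to Week 12 (Weeks 1, 2, 4, 6, 8, 12), with only Week 12 missing. Let R² = 5ρ²/(1 + 4ρ). The arm's variance factor is (1 − R²)/9 + R²/10. For ρ = 0.3, R² = 0.2045, the factor is 0.1088 and √[(0.1088 + 0.1)/0.2] gives +2.2%. For ρ = 0.9, R² = 0.8804, the factor is 0.1013 and the increase is +0.3%.
- Linear dose-response model, doses 0, 45, 90 and 180 mg, mean dose 78.75, Sxx = 177,187.5. Removing one value at dose d reduces Sxx by (40/39)(d − 78.75)². The slope SE rises by 0.04% (90 mg) to 3.1% (180 mg). The SE of that arm's predicted mean rises by a factor 1/√(1 − h), where h = 1/40 + (d − 78.75)²/Sxx: from 1.3% (90 mg, h = 0.0257) to 4.4% (180 mg, h = 0.0829).

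**5. Frequency.** The documents give no rate. If 3–10% of Week 12 assessments were out of allowance (an assumption), 40 × 0.03 = 1.2 to 40 × 0.10 = 4 would be excluded.

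**The case against.** The exclusion is pre-specified and stated in two places, and it keeps Week 12 close to a fixed interval after the last dose. The MMRM still uses the subject's other visits. The study is double-blind, nothing suggests that lateness differs by arm, and a 10-point shift sits inside intervals more than 75 points wide. All of that stands. It limits the size of the point, but it does not supply the missing scoring rule or explain why a scheduling tolerance should decide which outcomes are analysed.

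Two textual defences fail. The exclusion bullet in SAP 11.4.3 sits under data listings, but its words cover statistical analyses and SAP 11.2 has the same effect on summarised data. Reporting by nominal time does not help a value that is assigned to no nominal visit.

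Three stronger readings may tempt a reader, and the documents do not support them.
- *The SAP departs from the protocol's observed-case dataset.* Observed case may mean only that nothing is imputed, and Protocol 9.4.4 delegates the details to the RAP. The statement of no change in SAP 2.1 is not shown to be wrong.
- *The EULAR rules contradict each other.* They can be read in sequence: the three-level category is missing (SAP 11.5.4), then the binary responder (SAP 9.1.4) is imputed as failure (SAP 11.6.2, which names this endpoint). One linking sentence is needed.
- *The rules for several values conflict.* Read literally, SAP 11.2 applies to more than two assessments and SAP 11.5.1 to two. The two-value case is settled by SAP 11.5.1. What remains is untidy drafting.

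**Conclusion.** The point holds, at modest size. A scheduled efficacy assessment outside its allowance is excluded from the summaries and models, and its scoring in the responder endpoints is not stated. If it is treated as missing, a measured responder becomes a failure in ACR response, remission and EULAR response, at 10 points per subject in an arm of 10. For DAS28(CRP) and the other continuous endpoints the cost is a few per cent of a standard error.

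The reach is limited to secondary and exploratory efficacy estimates. No hypothesis is tested, so the harm is to estimates and their traceability. Non-compartmental PK parameters use actual sampling times (SAP 7.1.3.1). Adverse event summaries, respiratory events and re-tested laboratory items are not affected. A reader might infer a bias for or against the drug; the documents give no basis for either direction.

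The conclusion rests on the reading of the allowance row in step 2. The responder counts, correlations and out-of-allowance rates are assumptions. A figure in SAP 11.2 is not visible in the text reviewed, and the Protocol Deviation Management Plan was not available.

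**What to change.** Amend the SAP before unblinding:

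1. In SAP 11.2 and 11.4.3, define pre-specified, non-overlapping, capped efficacy analysis windows separate from the scheduling allowances. The sponsor sets the widths.
2. Analyse the assessment recorded in the eCRF for a scheduled visit when it falls in that window. State that for efficacy endpoints this overrides the SAP 11.2 rule that lists out-of-allowance data as unscheduled; without that sentence the Day 89 value would stay excluded. Truly unscheduled and early-withdrawal records stay as now.
3. Report the strict-allowance analysis as a sensitivity check, with the number of out-of-allowance assessments by arm and visit.
4. For binary endpoints, impute failure for missing data only when no assessment exists in the analysis window, so that a value beyond the cap counts as missing. Leave early withdrawal as failure unchanged. Add to the EULAR text in SAP 11.5.4 that a missing category counts as non-response in the binary analysis, in line with SAP 11.6.2.
5. Minor: merge the multiple-value rules of SAP 11.2 and 11.5.1 into one rule for any number of values.

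The cost is SAP wording and one visit-mapping step, with no new data. The downside is more spread in assessment day and in time since the last dose. Illustrating with ±7 days and a dose on Day 71, the interval becomes 7–21 days (78 − 71, 92 − 71) instead of 11–17 (82 − 71, 88 − 71). With the ±3-day dosing allowance (Days 68–74) it becomes 4–24 days (78 − 74, 92 − 68) instead of 8–20 (82 − 74, 88 − 68).

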5.4.2. QTc Stopping Criteria

- The QT interval corrected for heart rate according to Fridericia's formula (QTcF) *must* be used to determine eligibility for and discontinuation from the study.

- The QTcF must continue to be used for that subject *for all QTc data being collected for data analysis*. Safety ECGs and other non-protocol specified ECGs are an exception.
- The QTc should be based on single or averaged QTc values of triplicate electrocardiograms obtained over a brief (e.g., 5-10 minutes) recording period.

A subject who meets either of the bulleted criteria below will be withdrawn from the study:

- QTc >500 msec OR uncorrected QT >600 msec
- Change from baseline of QTc >60 msec

For subjects with underlying **bundle branch block**, follow the discontinuation criteria listed below:

Baseline QTc with bundle branch block	Discontinuation QTc with bundle branch block
< 450 msec	> 500 msec
450 – 480 msec	≥ 530 msec

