## 1.1. RAP Amendments

Revision chronology:

RAP Section	Amendment Details
Reporting and Analysis Plan_Study201789_Final [23-MAY-2017]	
Reporting and Analysis Plan_Study201789_final_Amend 1 [04-OCT-2017]	
Section 3.1 and Section 3.2	Removed these sections because the planned interim analyses have been canceled.
Section 3.3	Removed this section and added the unblinding process.
Section 3.1	Removed "(interim and final)".
Section 8.2.1	Added the listing of change from baseline in DAS28(CRP)
Section 9.1	Added the listings of ACR response, Categorical DAS28 response and DAS28 remission
Section 9.1	Added the listing of change from baseline in DAS28(ESR)
Section 11.4.3	Removed the Reporting area for interim analyses
Section 11.4.3	Amended the area for final reporting
Section 11.10.1	Amended the Numbering according to the change of the TLF.
Section 11.10.2	Removed the delivery description for interim analyses
Section 11.10.3, Section 11.10.4, Section 11.10.5, Section 11.10.6 and Section 11.10.12	Removed the TOC of TLF for interim analyses.
Section 11.10.9 and Section 11.10.10	Amended the TOC to simplify it.
Section 11.10.11	Amended the typos.
Section 11.10.12	Added the listings of ACR20/50/70, Categorical DAS28 response and DAS28 remission
Reporting and Analysis Plan_Study201789_final_Amend 2 [24-Jan-2018]	
Section 4.	Removed "valid" to avoid misunderstanding.
Section 6.1.3.	Added the description of RF and ACPA analyses.
Section 7.1.3.2.	Added one pharmacokinetic parameter "AUC(0-t)" for dose proportionality.
Section 7.2.1.	Added 3 AESI listings (Infection, Hypersensitivity Reactions and Injection Site Reaction)
Section 8.1.1.	Removed the summary of change from baseline in Borg scale because this variable is categorical.
Section 8.1.3.	Added the details of Immunogenicity analyses because of clarification of data in detail
Section 11.2.	Clarified that early withdrawal visits will be included for Assessment Windows.
Section 11.5.2	Added the reference date for Age calculation
Section 11.5.2	Added the definitions of Age Group and Age Category
Section 11.5.2	Amended the procedure for average daily dose of OCS to calculate it at only each scheduled visit.
Section 11.5.3	Amended the specification of AESI because the procedure to specify AESI was changed.
Section 11.5.4	Clarified that when calculating ACR, Patient's Assessment for Arthritis Pain "at this time" will be used.
Section 11.5.4	Amended the typos in SJC and TJC section.

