## 11.5. Appendix 5: Derived and Transformed Data

### 11.5.1. General

Multiple Measurements at One Time Point

 
Mean of the measurements will be calculated and used in any derivation of summary statistics but if listed, all data will be presented.
 
If there are two values within a time window the value closest to the target day for that window will be used. If values are the same distance from the target then the mean will be taken.
 
Subjects having both High and Low values for Normal Ranges at any post-baseline visits for safety parameters will be counted in both the High and Low categories of “Any visit post-baseline” row of related summary tables. This will also be applicable to relevant Potential Clinical Importance summary tables.
 

Study Day

 
Calculated as the number of days from randomization date : 
 
Ref Date = Missing → Study Day = Missing
 
Ref Date < Randomisation Date → Study Day = Ref Date – Randomisation Date
 
Ref Date ≥ Randomisation Date → Study Day = Ref Date – (Randomisation Date) + 1
 
 
 

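### A subject who leaves before Day 82 adds no post-baseline ECG and no treatment-period FEV1, FVC or DLCO to the safety summaries, and an ECG that triggers a QTc stop during dosing is only listed

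*SAP*

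**What the plan says.** **Unscheduled visits (SAP 11.4.3).** The rule is: "Unscheduled visits will not be included in summary tables, except for the Respiratory events and the laboratory items which may be re-tested". Figures exclude them as well. For listings: "All unscheduled visits will be included in listings". Visits outside the protocol windows "will be included in listings but omitted from figures, summaries and statistical analyses".

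**Allowances (SAP 11.2).** Data outside an allowance are not placed at a visit and "will be listed as unscheduled and early withdrawal unless otherwise specified". Where an allowance holds several assessments, "the first assessment will be treated as the scheduled and the others as the unscheduled".

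**Early withdrawal.** The amendment log (SAP 1.1) records: "Clarified that early withdrawal visits will be included for Assessment Windows". SAP 11.6.1 keeps the available planned data of withdrawn subjects in tables and figures unless another rule says otherwise. The Time and Events table (Protocol 7.1, repeated in SAP 11.1.1) has an early-withdrawal column but gives it no day or allowance.

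**A second rule for multiple values (SAP 11.5.1).** "If there are two values within a time window the value closest to the target day for that window will be used".

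**Schedule (Protocol 7.1).** After dosing starts, the ECG is planned only at Week 12 and at early withdrawal. Spirometry and DLCO are planned only at Week 12, follow-up and early withdrawal.

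**QTc rule (Protocol 5.4.2).** "A subject who meets either of the bulleted criteria below will be withdrawn from the study".

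**The concern.** ECG and vital signs are secondary safety endpoints, and Protocol 7.4.11 treats pulmonary assessment as central to safety monitoring. Protocol 9.4.2 promises summaries of the other safety parameters at each assessment visit. With only one on-treatment measurement planned for ECG, spirometry and DLCO, a rule that looks like routine by-visit housekeeping decides whether an early leaver is represented in those tables at all.

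For QTc the omission is tied to the outcome. Meeting the criterion forces withdrawal, and withdrawal before Week 12 removes the subject's only route into the ECG summaries. The tables could then describe only subjects who reached Week 12 without saying so.

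**Working it through.** **1. The plan's own figure.** Protocol Table 4 gives exact 95% limits for 10 subjects. The Clopper-Pearson limits are: lower = 0.025 quantile of Beta(x, n-x+1); upper = 0.975 quantile of Beta(x+1, n-x). For x = 1, 2 and 3 these give 0.25-44.50%, 2.52-55.61% and 6.67-65.25%, which agree with the printed table.

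**2. Early-withdrawal days that fall in an allowance.** The inputs are the days and allowances in the Time and Events table. Possible early-withdrawal days before the Week 12 slot opens are Days 2 to 81, which is 80 days.

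| Assessment | Slots in the treatment period | Days 2-81 inside a slot |
|---|---|---|
| ECG, FEV1, FVC, DLCO | Day 85 ±3, i.e. Days 82-88 | 0 of 80 |
| Assessments at every dosing visit | Days 8, 15, 22, 29 (±1); 43, 57, 71 (±3) | 4×3 + 3×7 = 33 of 80 (41%) |

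The vital-signs row is misaligned in the extracted text. If Day 71 is not a vital-signs visit, the second count is 33 - 7 = 26 of 80 (33%). An in-allowance early-withdrawal value is still set aside under the SAP 11.2 rule if a scheduled value came earlier in the same allowance.

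**3. Follow-up.** Protocol 5.4 places the leaver's follow-up visit 10 weeks (70 days) after the withdrawal visit. The scheduled slot is Day 155 ±7, i.e. Days 148-162. Early withdrawal + 70 ≥ 148 requires early withdrawal on Day 78 or later. If slotted by day, the follow-up spirometry and DLCO of anyone leaving before Day 78 are also out of window. No ECG is planned at follow-up.

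**4. QTc stop during dosing.** The last dose is on Day 71 and the only dated post-baseline ECG is at Days 82-88. A stopping value found during dosing must therefore come from an unscheduled or early-withdrawal ECG, and neither reaches Tables 3.13-3.15.

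**5. Size.** The documents give no expected number of early leavers. The illustration below assumes 0, 1 or 2 in an arm of 10 and no abnormal ECG among those who remain. The upper limit is 1 - 0.025^(1/n).

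| Leavers before Day 82 | Contributing to the ECG summary | Exact 95% CI |
|---|---|---|
| 0 | 0/10 | 0-30.85% |
| 1 | 0/9 | 0-33.6% |
| 2 | 0/8 | 0-36.9% |

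If the one leaver had a QTc stop, the full count would be 1/10 (0.3-44.5%) where the table shows 0/9. This comparison applies only to a count table, in practice Table 3.13. Tables 3.14, 3.15, 3.22-3.24 and 3.26-3.28 summarise values and changes, and there the loss is one contributing subject in 10.

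**The case against.** The strongest reply is that a reader could infer too much from these rules. They do not say that early-withdrawal results are excluded as such. SAP 11.2 removes only data outside an allowance, the amendment log brings early-withdrawal visits into the windows, and SAP 11.6.1 keeps planned data from withdrawn subjects. Nor do early leavers drop out of every safety table. Vital signs, cough, auscultation, oximetry and Borg scores are collected repeatedly, so scheduled values before withdrawal stay in. These points stand and limit the concern to the sparse assessments.

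It is also tempting to link the omission to stopping rules in general, which the documents do not support. Of the listed withdrawal criteria, only QTc rests on a measurement in the affected tables. A DLCO fall is not on the list, persistent cough or dyspnea leads to suspension (Protocol 5.5.1), and confirmed PAP is an adverse event of special interest with its own summary.

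The signal also has other routes. Clinically significant abnormalities become adverse events (Protocol 7.4.4), those leading to withdrawal are tabulated (Table 3.8), and persistent DLCO decline (Table 3.29) is exempt from the exclusion. About 40 subjects can be read in full from listings, and the study tests no hypothesis. This reduces the harm but does not remove it. The adverse event route depends on the investigator's judgement. Table 3.29 requires a fall of more than 15% sustained for at least 15 days, so a single large fall at withdrawal is summarised nowhere. Keeping unscheduled values out of by-visit means is sound practice, but it does not argue against a separate row.

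**Conclusion.** The concern holds for ECG, FEV1, FVC and DLCO. Anyone whose early-withdrawal visit is before Day 82 contributes no post-baseline ECG and no treatment-period spirometry or DLCO to the summaries. An ECG that triggers the QTc rule during dosing is listed but not summarised. Each such subject is 10% of an arm. For vital signs and oximetry the loss is at most the last or an unscheduled value. The outcome-linked omission is established for QTc only; for lung function, its direction depends on why subjects leave.

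The SAP's early-withdrawal handling is also unclear. Sections 11.2 and 11.6.1 can be read differently for a visit that is planned but has no allowance, and 11.2 and 11.5.1 choose different values within one window.

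This rests on the Time and Events days as extracted and on slotting by day. A figure in SAP 11.2 and the display shells (EG1, SAFE_T1, SAFE_T2) were not available. If they already provide an early-withdrawal or worst-value row, the remedy reduces to saying so in the text. SAP 11.5.1 mentions an any-visit post-baseline row, but for normal-range and potential-clinical-importance tables.

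**What to change.** 1. Add an early-withdrawal row and a row for any time post-baseline / worst value to the ECG, FEV1, FVC and DLCO tables (3.13-3.15, 3.22-3.24, 3.26-3.28). Both should include out-of-window early-withdrawal values, and the worst-value row unscheduled values too. Vital signs and oximetry are optional.
2. Leave the by-visit rows as they are. Do not move early-withdrawal values to the nearest scheduled visit: with Week 12 as the only treatment-period slot, an early ECG or DLCO could be labelled Week 12.
3. Reconcile SAP 11.2, 11.5.1 and 11.6.1: state when an early-withdrawal value counts as planned data, and use one rule for several values in a window.

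The cost is SAP wording and one or two rows per table, with no new data. The worst-value row mixes exposure durations and should be labelled so.
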